15.0 Monitoring Randomization Assignments and Data Safety Monitoring Board

Throughout the course of the study, the study's senior statistician will evaluate unblinded randomization assignments to assess the equivalence of the two groups. If the randomized groups are not matched, the randomization procedures may be altered to ensure that the two groups do not differ on relevant variables.

Each investigative site will have site specific **Data Safety Monitoring Board (DSMB)** which will be responsible for data and safety monitoring for each site. DSMB is responsible for reviewing study procedures, AEs, safety mailings (if applicable), enrollment, active subject progress, drop-out rates, and ongoing conduct of the research. The DSMB members can ask questions and make comments and/or recommendations to the investigators. The Institutional Review Boards (IRB) and SMC's are notified of significant findings by way of the DSMB meeting minutes at the time of continuing review according to each site's standard operating procedures. DSMB members must consist of physicians and scientists not listed as site investigators on this study. Data on the number of subjects enrolled and the number of AEs will

be reviewed by the DSMB at least bi-annually and more frequently if needed. The resulting report will be issued to the site specific IRBs and SMC at least at the time of IRB continuing review or more frequently by request. Any unanticipated events will be immediately directed to the lead investigators at each site who will follow their IRB reporting procedures.

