4.0 Study Design

One hundred and seventy-five subjects (N=70 HSV-1 seropositive and N=105 HSV-1 seronegative) will be randomized 1:1 to receive adjunctive valacyclovir or adjunctive placebo for a 16 week period. The primary outcome that will be assessed is improvement in changes in visual and working memory scores in HSV-1 positive and negative subjects over the course of the study. We will also measure the overall cognitive functioning and the severity of psychiatric symptoms over the course of the study and will evaluate the tolerability and safety of valacyclovir treatment in this population. In addition, we will explore the relationship between changes in the levels of inflammatory markers (HSV2, CMV, EBV, CRP, and Toxoplasmosis) and treatment response over the course of the study.

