The MCCB will be administered according to Attachment 1. It is a reliable cognitive battery (test-retest reliability ~0.7 for most tests. Small but statistically significant practice effects have been noted with speed of processing and problem-solving subtests (1/5th of standard deviation). To overcome these practice effects, alternate forms of MCCB will be implemented in this study. The total average administration time of MCCB is approximately 75 minutes. MCCB is comprised of seven cognitive domains and 10 related tests (Trail Making Test: Part A; Brief Assessment in Cognition in Schizophrenia: Symbol Coding; Hopkins Verbal Learning Test-Revised; Wechsler Memory Scale-Third Ed: Spatial Span; Letter-Number Sequencing; Neuropsychological Assessment Battery: Mazes; Brief Visuospatial Memory Test-Revised; Category Fluency: Animal Naming; Mayer-Salovey-Caruso Emotional Intelligence Test: Managing Emotions; and Continuous Performance Test-Identical Pairs. For each cognitive test, a multi-item score will be derived based on the raw item values according to the MCCB scoring manual. Each of the individual item raw scores is standardized to age- and gender-corrected t-scores (mean=50, standard deviation=10). Each test will be converted in to a domain score, with Working Memory and Speed of Processing domains consisting of 2 and 3 tests, respectively. The visual and working components of the MCCB will be administered first because they represent the primary aims of the study.²²

UCSD Performance-Based Skills Assessment-B (UPSA-B)

The UPSA-B is a performance-based assessment of improvement in functional capacity. Participants are asked to role-play tasks in 2 areas of functioning: communication and finances. The communication subtest revolves around a series of 9 role-play exercises using an unplugged telephone. The finance subtest tests the patient's ability to count change, read a utility bill, and write checks. Scores are assigned for each of the 2 subscales and a provided formula is used to calculate an UPSA-B Total Score (range = 0-100).²³

Personal and Social Performance Scale (PSP)

The PSP scale is a 100-point, single item, clinician rated scale to assess 4 domains of functioning, including personal and social relationships, socially useful activities, self-care and disturbing and aggressive behaviors.²⁴

Quality of Life Enjoyment and Satisfaction Questionnaire – Short Form (Q-LES-Q-SF)

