11.0 Laboratory Assessments

Study associated laboratory assessments (blood and urine) will be collected at time points specified in Study Procedures Table (Attachment 1) and analyzed by a local laboratory with the exception of the urine dipstick assessments which will be collected and analyzed onsite

A total of 36 mL of blood will be collected for screening assessments (Visit 1), 30 mL of blood will be collected at Visits , 6, and 10.

Laboratory assessments to be completed:

1. complete blood count with differential (CBC w/diff)
2. comprehensive metabolic panel (CMP)
3. uric acid level
4. creatinine clearance
5. calcium
6. lipid panel
7. hemoglobin A1c (HgbA1c)
8. thyroid stimulating hormone level (TSH)
9. pregnancy test (urine)
10. urine toxicology screen
11. urinalysis
12. hepatitis panel
13. serological assessment of antibodies to HSV1
14. inflammatory markers (HSV1, HSV2, EBV, HHV6, CMV, CRP, VZV, and Toxoplasmosis)

*All clinically significant abnormal laboratory findings subsequent to randomization will be repeated at appropriate intervals to establish resolution or until appropriate clinical follow-up can be established.

Serological Assessment of Antibodies to HSV1:

A serological assessment of antibodies to HSV1 will be completed by a central laboratory, Mayo Clinic Mayo Medical Laboratories, and results will be reported during the screening period prior to randomization for each subject. Results will be sent electronically to Indiana University Department of BioStatistics who will release the result to identified unblinded study personnel at each study site. The unblinded study personnel will be responsible for randomizing subjects to study treatment according to the stratified randomization block.

Inflammatory Markers

Inflammatory markers (HSV1, HSV2, EBV, HHV6, CMV, CRP, VZV, and Toxoplasmosis) will be assessed with methods previously described.²⁷ These serologic assessments will be performed centrally in [name] laboratory at the Johns Hopkins University School of Medicine. These blood samples will be de-identified at sites prior to sending for analysis. Study site investigators will remain blinded to the results of these assessments until after the trial has been completed.

Optional Repository Participation

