12.0 Study Medication/Treatment

Valacyclovir hydrochloride and matching placebo capsules will be used as study medication for this study. Placebo capsules will look like valacyclovir capsules, with matching shape, taste, and color. Subjects will be instructed to take 6 capsules of study medication daily.

The investigator or his/her designee is responsible for explaining the correct use of the study medication to the subjects, verifying subject understanding and agreement, maintaining accurate records of dispensing and collection, and destroying all unused medication according to their pharmacy standard operating procedures at the end of the study. Subjects will be instructed to contact the investigator as soon as possible if they have a complaint or problem with the study medication so that the situation can be assessed.

Method of Assignment to Treatment

Subjects who meet all criteria for enrollment will be 1:1 randomized in a double-blind fashion to adjunctive treatment with valacyclovir or placebo at Visit 2. Assignment to treatment groups will be determined by a computer-generated random sequence provided to sites by an unblinded biostatistics team at Indiana University. To minimize potential imbalance among treatment groups of factors that may influence efficacy outcomes, a stratified random assignment of subjects to therapy will be used to insure equal representation of HSV1 positive and negative subjects in the placebo and valacyclovir arms. The stratification factors used for this study include the investigative site.

Compounding and Pharmacy Oversight

Study medications will be sent to study sites at regular intervals from the University of Iowa which is contracted by Indiana University for preparation and shipping study medication for this study.

Study medication will be purchased directly through Indiana University. University of Iowa pharmacy will over-encapsulate the valacyclovir and create matching placebo capsules. Study medication will be stored according to the details on the product label (59° to 77° F).

Dosing

The dosing used in this study is 3 capsules of either valacyclovir or /placebo by mouth twice per day, given without regard to meals. Each valacyclovir capsule will contain 500 mg of active ingredient for a total daily dose of 3 grams per day. Dose reductions of 2 capsules per day will be permitted to address adverse events at the discretion of the site investigator.

Dispensing

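### Section 15 lets the randomisation procedures be changed during accrual with no stated rule; as a minor extra, site is a stratification factor that the analysis model does not name

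*Combined protocol and SAP*

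**What the plan says.** Section 4 fixes the ratio: subjects "will be randomized 1:1 to receive adjunctive valacyclovir or adjunctive placebo for a 16 week period". Section 12 gives the mechanism, "Assignment to treatment groups will be determined by a computer-generated random sequence", and its purpose, "To minimize potential imbalance among treatment groups of factors that may influence efficacy outcomes". It stratifies by HSV-1 status and adds: "The stratification factors used for this study include the investigative site". Section 11 indicates that the list is blocked, with unblinded staff "randomizing subjects to study treatment according to the stratified randomization block".

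Section 15 then says that "the study's senior statistician will evaluate unblinded randomization assignments to assess the equivalence of the two groups", throughout the study, and continues: "If the randomized groups are not matched, the randomization procedures may be altered to ensure that the two groups do not differ on relevant variables". The same section sets up site-specific DSMBs. They review study procedures and conduct and may make recommendations, but are given no approval role over randomisation.

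Section 12 does not mention that the sequence might change, and Section 16 does not say how a change would be analysed. The mixed model in Section 16 (Data Analysis) names baseline score, treatment, visit, HSV-1 status and their interactions, plus further baseline covariates that it does not list. Site is not named there, nor in the two-sample t tests, which the plan labels unadjusted.

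**The concern.** A stratified 1:1 list is normally fixed before the first subject enters. Here the procedure that produces it may be changed part-way, at someone's discretion, after the assignments have been seen. A reader of the final report could not tell what would have prompted a change, who would have decided it, or what the new scheme would have been. Any change would also divide the trial into periods before and after it, and the analysis has no term for period. What is at stake is whether the allocation can be reproduced and defended afterwards, in a trial whose intent-to-treat inference rests on it.

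The second matter is smaller and separate. When randomisation is stratified by site, the usual practice is to carry site into the model. Otherwise the standard error ignores balance that the design has already secured.

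**Working it through.** **What Section 15 specifies**

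| Element of a rule | Stated? |
|---|---|
| Who reviews | Yes, the senior statistician |
| When | Throughout the study; no schedule of looks |
| What counts as unmatched | No |
| Which variables | No |
| What replaces the current scheme | No |
| Who approves | No |
| How the analysis handles it | No |

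The nearest thing to a variable list is in Section 16, where demographics, symptom severity and antipsychotic dose equivalents are compared between arms by t and chi-square tests. That is for the baseline summary and is not linked to Section 15.

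**How often chance could invoke the clause.** The plan gives no figure to reproduce. The number of variables, the test, the looks and the block size below are all assumptions.

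One look, k independent variables, each tested at level p: P(at least one flagged) = 1 − (1 − p)^k.
- p = 0.05: 1 − 0.95² = 9.8%; 1 − 0.95⁵ = 22.6%; 1 − 0.95¹⁰ = 40.1%.
- p = 0.01: 2.0, 4.9 and 9.6%.
- p = 0.001: 0.2, 0.5 and 1.0%.

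Several looks, by simulation of correctly randomised trials of 175 (blocks of 4, two-sided t tests). Looks are at 44, 88 and 131 subjects. A look at 175 is excluded, because accrual is then complete and nothing is left to alter.

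| Test level | 2 variables | 5 variables | 10 variables |
|---|---|---|---|
| 5% | 21% | 44% | 69% |
| 1% | 5% | 12% | 22% |
| 0.1% | 0.4% | 1% | 2.5% |

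Repeat runs agree to within about two percentage points. The spread in the table comes entirely from choices that the plan leaves open.

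**The narrower reading.** Suppose the variables meant are only HSV-1 status and site. Five sites × two HSV-1 states give 10 strata. With assumed blocks of 4, a stratum can be out of balance by at most 2, so the seropositive arms can differ by at most 5 × 2 = 10. In simulation they differ by 1.6 subjects on average and by at most 4 in 95% of trials. With blocks of 6 the limit is 5 × 3 = 15, the mean 1.9 and the 95% point 5. On this reading the clause has little to do.

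**Site term.** From Section 16: 5 sites, 70 seropositive and 105 seronegative subjects, d = 0.63, and 0.05 per outcome one-sided. For scale, d = 0.63 with 35 per arm gives 83.3% power at one-sided 0.05 in a plain t test; the plan states no power.

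Assumptions:
- The baseline-to-follow-up correlation is 0.7. Section 8 gives "test-retest reliability ~0.7 for most tests", which is a reliability and not this trial's correlation.
- d applies to the residual SD, so the raw effect is 0.63 × √(1 − 0.7²) = 0.63 × 0.714 = 0.45 SD.
- There is one post-baseline score with complete data, and all 175 subjects are in the model.
- The site shares are as shown in the table.

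| Site variation | Share | Power without site | Power with site |
|---|---|---|---|
| Persistent level | 0% | 84.2% | 84.1% |
| | 5% | 83.7% | 83.7% |
| | 10% | 83.5% | 83.8% |
| | 20% | 84.0% | 84.6% |
| Change from baseline (share of residual variance) | 5% | 84.4% | 85.1% |
| | 10% | 84.9% | 86.7% |
| | 20% | 86.5% | 89.7% |

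The gain is under 1 point when sites differ only in level. It is 0.7, 1.8 and 3.2 points when they differ in change. Across repeated runs, one-sided type I error without site is about 0.036 to 0.05, at or below nominal; with site it is close to 0.05.

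**The case against.** The best defence is that the clause speaks of assignments and equivalence of the groups, never of outcomes. Balancing allocation on baseline variables is a recognised approach and does not itself bias the treatment comparison. Monitoring is sensible here, because Section 12 (Dispensing) leaves randomising to local pharmacies or unblinded site staff. The DSMBs do review study procedures, so oversight is not absent. All of this stands. It does not supply the missing rule, and reviewing procedures is not approving a change to allocation.

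It is also fair to say that the trigger rates measure no harm. They show how often an assumed test on an assumed number of variables would cross a line.

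A reader might infer that the clause inflates type I error. One can construct such a case: if allocation moved from 1:1 to between 1.5:1 and 3:1 halfway through the 70 seropositive subjects, with an outcome drift of 0.2 to 0.4 SD and no period adjustment, a one-sided 0.05 test would run at about 0.059 to 0.113. The documents do not support this as a finding. Sections 4 and 12 state 1:1, nothing proposes another ratio, and the drift is invented.

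On site, the unlisted baseline covariates might already include it, and the t tests are unadjusted by design. Both points are right, which is why this part is minor.

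**Conclusion.** The gap in Section 15 is real and should be closed. It is a defect of pre-specification: a discretionary change to allocation, made with assignments visible, has no stated trigger, variables, scheme, approver or analysis. The plan does not show bias, and it does not say that the statistician would see outcomes or that the ratio would move; none of these should be read into it. How often chance would invoke the clause cannot be known from the documents. Under the assumed criteria the three-look figure runs from about 0.4% to 69%.

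The site point is a minor improvement. Omission is mildly conservative and does not invalidate the analysis. The gain from naming site is between nothing and about 3 points of power, and rests on assumed site shares of up to 20%, an assumed correlation of 0.7 and d = 0.63 taken on the residual SD.

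**What to change.** **Section 15.** Replace the sentence on altering the procedures with wording such as: *The 1:1 list stratified by HSV-1 status and site is fixed before first enrolment and is not changed because of observed baseline differences. Monitoring checks that the list is correctly generated and implemented; errors in generation or implementation are corrected and logged, and subjects are analysed as randomised.*

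If the sponsor wants to keep the option to adapt, an acceptable alternative is to pre-specify the variables, the threshold, the replacement scheme, an independent approver and the handling in the analysis.

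The cost is one replaced sentence. The downside is that some chance imbalance may remain in the baseline table; the planned model already adjusts for the baseline score.

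**Section 16 (minor).** Name site (5 levels) as a fixed effect in the mixed model. The cost is 4 degrees of freedom: 175 − 5 = 170 becomes 175 − 9 = 166 in the single-visit model used above. The unadjusted t tests can stay as they are.

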16.0 Statistical Analysis

Power analysis

The effect sizes observed in the completed Prasad et al. 2012 study were used to estimate the sample size necessary for adequate power to detect differences in cognitive variables for the current study. The earlier study, which enrolled 12 patients in each group, saw changes in cognitive function with effect sizes that ranged from small ($d=0.25$) to quite large ($d=1.21$). An intent-to-treat (ITT) analysis will be adopted, which includes all randomized subjects. We will use two cognitive domains from the MATRICS battery, visual memory and working memory, as the primary outcome variables. Prasad reported effect sizes of Cohen's $d=0.79$ for working memory and $d=0.97$ for visual object learning when comparing valacyclovir to placebo in HSV-1-seropositive subjects. Forty percent of patients with schizophrenia are HSV-1 positive (Prasad et al in press; Dickerson et al 2003). A total of 175 subjects will be enrolled at 5 sites, with the expectation that 70 subjects will be HSV-1-seropositive and 105 subjects will be seronegative. With 70 HSV-1 positive subjects enrolled (35 per treatment group), we would be able to detect a minimum effect size of $d=0.63$ (a conservative estimate based on the Prasad study) for each of the two primary outcome measures at significance level $\alpha=0.05$ using two-sided t tests. The Hochberg modification of the Bonferroni method to control Type 1 error will be used. With this method, the smallest of the p-values for the two outcomes is tested at $p<\alpha/2$; if that test is rejected, the second outcome is tested at $p<\alpha$. We will achieve the same power when testing HSV-1 positive vs. negative subjects who are on valacyclovir using similar methods. We will test the treatment effects on the two primary efficacy measures (visual and working memory) with one-tailed tests at an overall $\alpha=0.1$. Stratified randomization will be used to ensure the balance of HSV-1 status between the valacyclovir group and the placebo group.

Data Analysis

The primary objective of this study is to determine: 1) whether valacyclovir improves cognitive functioning in schizophrenia subjects who are HSV1 seropositive and early in the course of their illness, and 2) whether the improvement from valacyclovir differs in HSV1 seropositive and negative subjects. We hypothesize that subjects who received valacyclovir will show improvement in memory functioning, as measured by the visual and working memory domains of the MATRICS cognitive battery relative to their counterparts who received placebo, and the improvement exists in HSV-1 seropositive subjects compared to the seronegative subjects. All randomized subjects will be used using ITT analysis. This is the most conservative approach for detecting a treatment effect, because the inclusion of subjects who did not complete the intervention will serve to underestimate rather than overestimate any treatment effect. Sensitivity analyses including a subset analysis using completers only analysis will also be performed to test the robustness of the findings. Statistical tests will be performed based on one-sided test at the 10% level of significance with an adjustment for multiple comparisons for the 2 primary efficacy outcome measures with each primary measure tested at an alpha threshold of $p<0.05$ as noted above. One-tailed tests are planned because the main interest of this study is to

determine if valacyclovir is superior to placebo and thus has produced a sufficient efficacy signal in one or more of the two primary efficacy outcome measures to warrant further assessment in subsequent larger, confirmatory trials.

Baseline analysis will be conducted to summarize patients' characteristics in the two treatment groups for HSV-1 seropositive and seronegative subjects respectively. Demographics and relevant clinical variables, including symptom severity and antipsychotic dose equivalents, will be compared between treatment groups using two-sample t tests (for continuous variables) and chi-square tests (for categorical variables).

The primary outcome measures are the visual and working memory domains of the MATRICS battery. For each subject, a change score will be calculated for this domain, which quantifies the difference in cognitive performance from pre-treatment baseline to post randomization study visits. Unadjusted p-values from direct comparison of valacyclovir vs. placebo among HSV-1 positives, and HSV-1 positive vs. negative with active treatment will be reported using two-sample one-sided t tests.

The primary outcome measures (visual memory and working memory) and important secondary cognitive (MCCB composite score) and functional (UPSA-B, Q-LES-Q-SF) outcome measures will be assessed at baseline, visit 6 and visit 10. To analyze these measures, we will employ a mixed model for repeated measures ANCOVA, of the general form for each measure: Post-baseline score at visit i = baseline score + treatment + visit + HSV-1 status + interactions among treatment, visit, and HSV-1 status + other baseline covariates, where visit is a categorical measure denoting whether the post baseline score came from visit 6 or 10. Within-subject correlation will be modeled with an unstructured covariance matrix with 3 parameters (variances at visit 6 and 10, covariance between visits 6 and 10). In this model, the treatment effect estimates the average magnitude of the treatment differences at visits 6 and 10, and the treatment x visit interaction the difference in the magnitude of the treatment difference at visit 10 vs visit 6. Additional interactions involving treatment, HSV-1 and week estimate how the magnitude of treatment differences, on average or at visits 6 versus 10, is altered by HSV-1 status. No imputation will be needed to address missing data issue using the linear mixed model approach.

For PANSS scores, which are assessed at 4 post-baseline visits, we will also use mixed model ANCOVA with a similar set of fixed effects, but will compare the fit of linear or higher order polynomials to estimate time trends in treatment effects. In past studies in schizophrenia using the CGI, we have observed that 1) most values are clustered tightly among 3 or 4 of the 7 possible grades of severity, and 2) few subjects change more than 1 or 2 points. These features that suggest linear mixed models may be inappropriate for detecting change in the CGI. Accordingly, we will assess change in the CGI as follows: 1) For each subject, we will compute the Spearman rank correlation between visit number and CGI score for all visits observed, as a nonparametric measure of trend; and, 2) a Wilcoxon test will be used to compare the average magnitude of within-participant Spearman trend scores a) between all participants on Valacyclovir and Placebo; b) between participants on are HSV-1 seropositive and on valacyclovir or placebo; or, c) between participants on are HSV-1 sero negative and on valacyclovir or placebo. We will use multiple imputation of missing CGI data to assess the sensitivity of these analyses to missing data.

Another analysis objective is to assess the safety and tolerability of valacyclovir treatment in this patient population. Safety data will be analyzed using incidence density analysis to compare the rates of adverse events (AEs) across groups. Incidence density analysis is ideal for adverse events comparisons, because event frequencies are adjusted for the total duration of follow-up, and thus corrects for different rates of follow-up between study groups. The occurrence of all adverse events will be compared, as will the occurrence of the following categories of adverse events: total AEs, serious AEs, psychiatric AEs, and AEs grouped by organ system. Survival analysis techniques will also be employed to compare retention time across groups. In addition, secondary analyses will include testing for drug versus placebo effects in all participants without consideration of HSV-1 sero status. All statistical analyses will be conducted using SAS 9.1.

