10.0 Criteria for Repeat Assessments, Rescreening, and Discontinuation

Repeat Assessments

Screening assessments can be repeated within the screening window under the same screening number with the exception of eligibility criteria related rating scales/questionnaires. Subject diagnosis confirmation will not be repeated.

Rescreening

Subjects who screen fail may be rescreened one time, under a new screening number. If a subject is rescreened, all screening assessments (with the exception of the diagnosis confirmation) must be repeated and the stability criteria timelines must be met.

Discontinuation

Subjects will be discontinued under the following circumstances:

1. Study Medication Non-Compliance: Significant noncompliance is defined as missing seven or more consecutive days of study medication or more than 24 cumulative days of study medication during the entire study.
2. Subjects who have the following lab values while on study medication:
 - Liver transaminase levels >3 times the ULN
 - Hemoglobin <9
 - White blood cells <1500
 - Serum creatinine >1.5
3. Subjects who develop moderate or severe renal impairment as defined by CrCl <50 ml/min (measured by the Cockcroft-Gault equation) while on study medication
4. Female subjects who become pregnant while on study medication
5. Subjects who require more than 50% increase in their dose of antipsychotic medication OR the addition of a new antipsychotic medication will be reviewed by the principal investigator and discontinuation will be addressed on a case-by-case basis as clinically indicated.
6. Subjects who require treatment with any excluded concomitant medications (See Attachment 2)

If a subject discontinues from the study, discontinuation assessments will be at the discretion of the investigator.

A subject may withdraw from the study medication at any time at his/her own request, or may be withdrawn at any time at the discretion of the investigator for safety, behavioral, or administrative reasons.

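### The only sensitivity analysis specified for the two primary memory outcomes is completers-only, and its agreement with the mixed model would not show robustness to dropout that depends on unobserved scores

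*Combined protocol and SAP*

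**What the plan says.** Section 16.0 (Data Analysis) sets the analysis population: "All randomized subjects will be used using ITT analysis". It defends this choice on the ground that "the inclusion of subjects who did not complete the intervention will serve to underestimate rather than overestimate any treatment effect". The check on that analysis is: "Sensitivity analyses including a subset analysis using completers only analysis will also be performed to test the robustness of the findings". The document does not define a completer.

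The memory outcomes "will be assessed at baseline, visit 6 and visit 10" and are analysed by a repeated-measures mixed model with unstructured covariance. Its treatment term averages the Visit 6 and Visit 10 differences. On missing data the section says "No imputation will be needed to address missing data issue using the linear mixed model approach", without stating the assumption this needs. For the CGI alone it adds: "We will use multiple imputation of missing CGI data to assess the sensitivity of these analyses to missing data". Retention time is also to be compared between groups.

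Section 10.0 lists reasons for discontinuation, including non-compliance: "Significant noncompliance is defined as missing seven or more consecutive days of study medication or more than 24 cumulative days". It then says: "If a subject discontinues from the study, discontinuation assessments will be at the discretion of the investigator". No dropout rate is given for this trial.

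**The concern.** The mixed model is valid when missingness depends only on observed data (missing at random). A completers-only ANCOVA needs that and more: given baseline and arm, dropout must also be unrelated to the Visit 6 score. A check that rests on the stronger assumption cannot test the weaker one. If loss depends on the unseen Visit 10 score, both analyses shift in the same direction by similar amounts and appear to confirm each other.

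Subjects who leave before Visit 6 without a later memory score supply no outcome data to either analysis, so comparing the two cannot address them.

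The argument that including non-completers makes the estimate conservative holds when their outcomes are measured. It does not follow when their scores are missing, and section 10.0 does not require those scores to be collected. At stake is the efficacy signal in about 35 HSV-1 positive subjects per arm, which is meant to decide whether larger trials are warranted. Agreement with completers-only would be reported as robustness.

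**Working it through.** **The plan's own figure.** The plan has no figure for dropout or missing-data bias to reproduce. Its nearest figure is a detectable d = 0.63 with 35 per arm, given without a power. By noncentral t, that is 73.8% power at two-sided 0.05 and 83.3% at one-sided 0.05. The point does not depend on it.

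**Inputs.** From the documents: 35 per arm (section 16.0); T-score SD 10 and test-retest reliability of about 0.7 (section 8.0, MCCB), used here as the correlation between any two of baseline, Visit 6 and Visit 10. Assumed: Visit 6 complete, 26% missing at Visit 10 in each arm, no true effect.

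**Loss model.** SD of change = 10 × √(2 × (1 − 0.7)) = 7.75 points. On drug, logit P(missing) = a − change/7.75, with a set to give 26%. On placebo, loss is random at 26%, or follows the same rule as on drug.

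**Estimates.**
- Mixed model: regress Visit 6 on arm and baseline in everyone (arm coefficient g). Regress Visit 10 on arm, baseline and Visit 6 in those observed (arm coefficient h, Visit 6 slope b). The Visit 10 effect is h + b × g. The planned average is (g + Visit 10 effect)/2.
- Completers: ANCOVA of Visit 10 on arm and baseline.

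**Mean bias in T-score points (6,000 simulated trials each).**

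| Loss depends on | Arms | Mixed model, Visit 10 | Mixed model, average | Completers, Visit 10 | Gap at Visit 10 |
|---|---|---|---|---|---|
| observed Visit 6 change | drug only | 0.0 | 0.0 | +0.6 | 0.6 |
| unseen Visit 10 change | drug only | +1.2 | +0.6 | +1.45 | 0.24 |
| either | both alike | 0.0 | 0.0 | 0.0 | 0.0 |

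From trial to trial the Visit 10 estimates have an SD of about 2 points, the average about 1.5, and the gap about 0.45 to 0.5. A mean gap of 0.24 is therefore lost in noise. Even the 0.6 gap in the first row is only a weak flag.

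**Effect on the planned test.** Bias/SD = 0.6/1.5 = 0.40. The chance of rejecting at a one-sided 5% level is 1 − Φ(1.645 − 0.40), about 0.11, so roughly 10% instead of 5%.

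**Other loss assumptions.** A large-sample run (400,000 per arm) let loss depend on the Visit 10 score itself with slope 1 per SD. Bias at Visit 10, mixed model against completers ANCOVA:
- opposite directions by arm, 20%/20%: +0.16 against +0.19 SD
- same direction, 30% on drug and 10% on placebo: +0.08 against +0.09 SD
- same direction, 20%/20%: about 0 for both

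**What a tipping-point analysis would show.** Suppose the estimate is 0.63 SD. SE = √(2/35) = 0.239, and the one-sided 5% threshold is 1.645 × 0.239 = 0.393. If a share p of the drug arm is missing and truly worse than the model predicts by δ, significance is lost at δ = (0.63 − 0.393)/p. That is about 2.37 SD for p = 10%, 1.18 SD for 20% and 0.79 SD for 30%.

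**The case against.** The strongest reply has four parts.

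- **The wording is open.** The sentence introduces completers-only with the word including, and retention time is compared elsewhere. A reader might infer that no other check is intended. The documents support only that no other is specified. The retention comparison is a useful dropout diagnostic but does not re-analyse memory scores.
- **Completers-only is not uninformative.** A reader might infer that it can reveal no missing-data bias, or that completers must be a simple random subset of each arm. Neither is right: a gap can flag loss related to Visit 6, and a completers ANCOVA stays unbiased when loss depends only on baseline and arm.
- **Arm-specific informative loss is not documented.** Section 2.0 lists headache, nausea and stomach pain as commoner on drug. It also reports similar dropout between arms in the pilot, and discontinuations for adverse events spread evenly across groups in a one-year study at lower doses. This stands as a limit on the illustration. Similar rates do not establish similar reasons, however, and the biased scenarios in the table use equal rates.
- **The CGI contrast is weak.** A reader might infer that the plan holds a secondary outcome to a higher standard. The CGI analysis uses within-subject rank trends and a Wilcoxon test, which have no likelihood-based handling of missing data, so imputation fills a gap there. Nothing says that imputation departs from missing at random.

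In a signal-finding trial one may call a tipping-point analysis desirable rather than essential. That bears on the priority of the change, not on whether the stated check does its job.

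**Conclusion.** The point holds as worded in the heading. Nothing specified for the primary outcomes examines departures from missing at random. The one named analysis makes a stronger assumption than the analysis it is meant to check, and the claim that non-completers can only dilute the effect does not follow when their scores are missing.

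Under the illustrated assumptions the mixed-model bias is about +1.2 points (0.12 SD) at Visit 10 and +0.6 (0.06 SD) for the planned average. It is about 0 when rate and mechanism are the same in both arms. These figures rest on an assumed loss rate and mechanism, complete Visit 6 data and a correlation of 0.7. A reader might infer that the trial's result will be biased in favour of valacyclovir. The documents do not show that; they show only that the plan could not tell.

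**What to change.** In section 16.0 (Data Analysis):

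1. Define completer, keep the completers-only analysis as descriptive, and remove its role as the robustness test.
2. State the mixed model's missing-at-random assumption, and qualify the sentence that says the bias can only be downward.
3. For visual and working memory in HSV-1 positive subjects, add two analyses in all randomised subjects: (a) a placebo-based imputation of missing valacyclovir scores, and (b) a delta-adjusted tipping-point analysis reporting the shift in unobserved valacyclovir scores at which the conclusion changes. Fix the range of shifts before unblinding.

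Ordinary imputation by arm from baseline and Visit 6 would largely repeat the mixed model, so it is not a substitute for (a) and (b).

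Cost: a paragraph of text, some programming and advance agreement on the shift range. No new data are needed.
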